16.1.1 Plasma Variables

16.1.1.1 Concentrations

- Plasma concentration of apaglutide

16.1.1.2 Parameters

- PK Parameters for apaglutide as defined in [Table 3: Plasma Parameters](#).

Table 3: Plasma Parameters

Parameter	Description	SAS Programming Notes
C_{max}	Maximum plasma concentration. Observed peak analyte concentration obtained directly from the experimental data without interpolation, expressed in concentration units	Cmax from WNL
AUC_{last}	Area under the concentration-time curve (time 0 to time of last quantifiable concentration).	AUC_{last} from WNL
AUC_{inf}	Area under the plasma concentration-time curve (time 0 to infinity). calculated as: $AUC_{0-inf} = AUC_{0-last} + (C_{last}/k_{el})$ where C_{last} is the observed concentration at the last time point with concentrations above the lower limit of quantification (LLOQ).	AUC_{inf_obs} from WNL If $AUC_ \%Extrap_obs > 20\%$ then parameter is flagged
AUC_{0-168h}	Area under the plasma concentration-time curve from time 0 to 168 hours post-dose.	AUC_{0-168} from WNL where partial time =168
t_{max}	Time to maximum plasma concentration. First observed time to reach peak analyte concentration obtained directly from the experimental data without interpolation, expressed in time units.	T_{max} from WNL
k_{el} (also denominated as λ_z)	Terminal phase rate constant calculated by linear regression of the terminal log-linear portion of the concentration vs. time curve. Linear regression of at least three points and an adjusted r^2 greater than or equal 0.80 are required to obtain a reliable k_{el} .	$\Lambda_{z_}$ from WNL If adjusted $Rsq < .80$ then parameter is flagged
$t_{1/2}$	Terminal phase half-life expressed in time units. Adjusted r^2 greater than or equal to 0.80 is required to obtain a reliable $t_{1/2}$.	HL_{Λ_z} from WNL If adjusted $Rsq < .80$ then parameter is flagged
CL/F	Apparent total clearance of the drug from plasma after subcutaneous administration	CL_F_obs from WNL
Vz/F	Apparent volume of distribution during the terminal phase after subcutaneous drug administration	Vz_F_obs from WNL

The PK parameters below will be listed only.

%AUCextra	Percentage of AUC_{0-inf} that is due to extrapolation from the time of last observed concentration to infinity.	$AUC_ \%Extrap_obs$ from WNL
Adj r^2	Goodness of fit statistic for the loglinear terminal elimination phase of the concentration time profile identified by least squares linear regression and adjusted	$Rsq_adjusted$ from WNL

	for the number of points (minimum of 3, excluding C_{max}) used in the estimation of K_{el}	
Kel_Start	The start time used in the regression for the determination of K_{el}	Lambda_z_lower from WNL
Kel_End	The end time used in the regression for the determination of K_{el}	Lambda_z_upper from WNL
Kel_N	The number of points used in the regression for the determination of K_{el}	No_points_lambda_z from WNL

Note: AUCs will be calculated using linear up / log down, expressed in units of concentration x time.

16.2 Pharmacokinetic Summaries

16.2.1 Pharmacokinetic Concentrations

Plasma concentrations for apaglutide below the quantifiable limit (BQL) will be set to ½ lower limit of quantification (LLOQ) in the computation of mean concentration values. Descriptive statistics (number of subjects, arithmetic mean, geometric mean, standard deviation (SD), coefficient of variation (CV), Geometric CV, median, minimum, and maximum) will be used to summarize the plasma concentrations by hepatic function group at each scheduled time point. If over ½ the subjects in a given cell have values BQL then the descriptive statistics will not be presented and will instead display as BQL for the mean and minimum. With the exception of maximum all other statistics will be missing. The individual plasma concentrations data will be presented together with the descriptive statistics.

Linear and semi-logarithmic plots of the geometric mean (including Error Bars) plasma concentration by scheduled sampling time will be provided by hepatic function group. These plots will show time in hours. The plots will match the summary table results and will not have an observation at a given time point if more than half of the subjects have values BQL.

Linear and semi-logarithmic plots of the individual plasma concentration by actual sampling time will be provided by subject. These plots will show time in hours. Individual plots will use the BQL handling procedure described below for "Pharmacokinetic Parameters".

Combined individual plasma concentrations both on a linear and semi-logarithmic scale versus actual sampling time in hours, showing all subjects together in a single plot, will be presented by hepatic function group.

16.2.2 Pharmacokinetic Parameters

PK parameters for apaglutide will be estimated using non-compartmental methods with WinNonlin®.

The plasma PK parameters will be estimated from the concentration-time profiles. In estimating the PK parameters, BQL values at the beginning of the profile will be set to zero. BQL values that occur after the first quantifiable point will be considered missing. Values that are embedded between BQLs, or quantifiable values occurring after two or more BQLs, will be set to missing at the discretion of the pharmacokineticist. Actual sampling times, rather than scheduled sampling times, will be used in all computations involving sampling times. If the actual time or dose time is missing, the scheduled time may be substituted in order to calculate the PK parameter.

Descriptive statistics (number of subjects, mean, geometric mean, standard deviation, coefficient of variation, Geometric CV, median, minimum, and maximum) will be used to summarize the calculated PK parameters by hepatic function group. For t_{max} , only median, min and max will be presented. The individual PK parameters will be presented together with the descriptive statistics.

The points to be included in the k_{el} range will be determined by the pharmacokineticist after inspection of the semi-log concentration-time profiles. At least 3 points will be required to be used. The C_{max} data point will not be included.

Parameters based on adjusted r^2 below 0.80 or %AUC_{extra} above 20% will be flagged but not excluded from descriptive statistics.

Box and whisker plots for individual subject parameters (AUC_{inf} or AUC_{last} and C_{max}) will be constructed by hepatic function group and overlaid with geometric means.

16.2.2.1 Statistical Analyses

Part 1:

Analysis of variance (ANOVA) will be used to compare the natural log transformed AUCinf or AUClast (if AUCinf cannot be calculated) and Cmax for apraglutide between normal hepatic function group (Reference) and the moderate impaired hepatic group (Test).

If there is a dropout in the moderate hepatic function group, the “matched” subject in the normal hepatic function group will be excluded from this analysis. The subject from the normal hepatic group may however be used in the analysis for part 2 if there is a matched Mild hepatic function group subject.

If the AUCinf is extrapolated by more than 20% for 1 subject, the AUClast should be used for all subjects for the determination of the Geometric Mean Ratio (GMR).

Estimates of the mean differences (Test-Reference) and corresponding 90% CIs will be obtained from the model. The mean differences and 90% CIs for the differences will be exponentiated to provide estimates of the GMR (Test/Reference) and 90% CIs for the ratios.

The following SAS PROC MIXED pseudo-code may be used:

```
proc mixed data = adpp;
  by parameter;
  class hepatic_group;
  model log(aval) = hepatic_group;
  lsmeans hepatic_group / cl alpha = 0.1;
  estimate "Moderate hepatic impairment vs Normal hepatic function"
hepatic_group 1 -1 /e cl alpha=0.1;
run;
```

Part 2 (if conducted):

Part 2 may be conducted if apraglutide AUCinf (or AUClast when AUCinf cannot be calculated) GMR for the moderate hepatic impairment group versus the normal group is ≥ 2 .

Analysis of variance will be used to compare the natural log transformed AUCinf or AUClast and Cmax for apraglutide between normal hepatic function group from Part 1 (Reference) and the mild impaired hepatic group (Test). Estimates of the mean differences (Test-Reference) and corresponding 90% CIs will be obtained from the model. The mean differences and 90% CIs for the differences will be exponentiated to provide estimates of the GMR (Test/Reference) and 90% CIs for the ratios.

The following SAS PROC MIXED pseudo-code may be used:

```
proc mixed data = adpp;
  by parameter;
  class hepatic_group;
  model log(aval) = hepatic_group;
  lsmeans hepatic_group / cl alpha = 0.1;
  estimate "Mild hepatic impairment vs Normal renal function" hepatic_group
1 -1 /e cl alpha=0.1;
run;
```

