All subjects will receive a single SC dose of apraglutide (5 mg). Apraglutide is supplied as a freeze-dried powder (12.5 mg) for reconstitution in sterile water prior to SC injection.

Each apraglutide treatment will be given on Day 1, within 30 minutes following a light breakfast.

Statistics

Hypothesis

No formal statistical hypotheses will be tested in the trial.

Sample Size Calculation

No formal power calculation was performed. The number of subjects per group is based on a review of the literature, and a review of the EMA and FDA guidelines.

The sample size of approximately eight subjects per group is also based on the feasibility to recruit subjects with various degrees of hepatic impairment.

Summary of Planned Analyses

Pharmacokinetic Analyses

Non-compartmental methods will be applied to compute the PK parameters. Plasma concentrations and computed PK parameters will be listed and summarized descriptively. Individual and mean plasma concentration versus time data will be presented graphically.

Part 1 of the Trial

Analysis of variance will be used to compare the natural log transformed AUC_{inf} or AUC_{last} (if AUC_{inf} cannot be calculated) and C_{max} for apraglutide between the normal hepatic function group (Reference) and the moderate hepatic impairment group (Test). Estimates of the mean differences (Test-Reference) and corresponding 90% confidence intervals (CI) will be obtained from the model. The mean differences and 90% CIs for the differences will be exponentiated to provide estimates of the ratio of the adjusted geometric means (Test/Reference) and 90% CIs for the ratios.

Part 2 may be conducted if apraglutide AUC_{inf} (or AUC_{last} when AUC_{inf} cannot be calculated) GMR for the moderate hepatic impairment group versus the normal group is ≥ 2.0 . Apraglutide is well tolerated up to 56.9 mg SC single dose as well as 28.4 mg SC weekly doses, further demonstrating the large therapeutic margin of apraglutide.

Part 2 of the Trial

Analysis of variance will be used to compare the natural log transformed AUC_{inf} or AUC_{last} and C_{max} for apraglutide between normal hepatic function group from Part 1 (Reference) and the mild hepatic impairment group (Test). Estimates of the mean differences (Test-Reference) and corresponding 90% CIs will be obtained from the

model. The mean differences and 90% CIs for the differences will be exponentiated to provide estimates of the GMR (Test/Reference) and 90% CIs for the ratios.

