2. OBJECTIVES

2.1. Primary Objectives

- Part 1: To assess the PK of apraglutide in subjects with moderate hepatic impairment compared with matched control subjects with normal hepatic function following single SC dose administration

- Part 2 (if applicable; see criteria to move to Part 2): To assess the PK of apraglutide in subjects with mild hepatic impairment compared with matched control subjects following single SC dose administration

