12.3.2. Key Elements of Analysis Plan

12.3.2.1. Pharmacokinetic Analyses

Non-compartmental methods will be applied to compute the PK parameters. Plasma concentrations and computed PK parameters will be listed and summarized descriptively. Individual and mean plasma concentration versus time data will be presented graphically.

Part 1 of the trial

Analysis of variance will be used to compare the natural log transformed AUC_{inf} or AUC_{last} (if AUC_{inf} cannot be calculated) and C_{max} for apaglutide between the normal hepatic function group (Reference) and the moderate hepatic impairment group (Test). Estimates of the mean differences (Test-Reference) and corresponding 90% confidence intervals (CI) will be obtained from the model. The mean differences and 90% CIs for the differences will be exponentiated to provide estimates of the ratio of the adjusted geometric means (Test/Reference) and 90% CIs for the ratios.

Part 2 may be conducted if apaglutide AUC_{inf} (or AUC_{last} when AUC_{inf} cannot be calculated) GMR for the moderate hepatic impairment group versus the normal group is ≥ 2.0 . Apaglutide is well tolerated up to 56.9 mg SC single dose as well as 28.4 mg SC weekly multiple doses, further demonstrating the large therapeutic margin of apaglutide.

Part 2 of the trial

Analysis of variance will be used to compare the natural log transformed AUC_{inf} or AUC_{last} and C_{max} for apaglutide between normal hepatic function group from Part 1 (Reference) and the mild hepatic impairment group (Test). Estimates of the mean differences (Test-Reference) and corresponding 90% CIs will be obtained from the model. The mean differences and 90% CIs for the differences will be exponentiated to provide estimates of the GMR (Test/Reference) and 90% CIs for the ratios.

Box and whisker plots for individual subject parameters (AUC_{inf} or AUC_{last} and C_{max}) will be constructed by hepatic function group and overlaid with geometric means.

For summary statistics and median/mean plots by sampling time, the nominal PK sampling time will be used. For individual subject plots by time, the actual PK sampling time will be used.

If Part 2 is executed and data for normal, mild and moderate impairment groups are available, additional analysis will be performed to assess the relationship among appropriate PK parameters and hepatic function.

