5.1.1 Primary Endpoint

- Area under the curve to infinity (AUC_{inf}) or area under the curve from time zero to the last quantifiable concentration (AUC_{last}) if AUC_{inf} cannot be reliably estimated.
- Area under the curve from time zero to 168 hours after apaglutide administration ($AUC_{0-168\text{hr}}$)
- Maximum observed plasma concentration (C_{max})

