7.2 Interim Analysis and Key Results

An interim PK report will be created by the pharmacokineticist.

After Part 1 the PK results will be sent by the PK lab to the pharmacokineticist. This will be sent per Data Transfer Agreements created by ICON Data management and will contain Quality controlled (QC'd) results. Based on these results the pharmacokineticist will calculate the required PK Parameters for the interim analysis based on nominal sampling time points. The PK parameters required for the interim reporting will be AUC_{inf} (or AUC_{last}) and C_{max} .

The interim report will contain the raw concentration data, a table with at least the primary PK parameters and a table showing the GMR point estimate of apraglutide AUC_{inf} (or AUC_{last}) and C_{max} for the moderate hepatic impairment group compared to the control group.

If the AUC_{inf} is extrapolated by more than 20% for 1 subject, the AUC_{last} should be used for all subjects for the determination of the Geometric Mean Ratio (GMR). If the GMR for the moderate hepatic impairment group versus the normal group is ≥ 2.0 , Part 2 may be conducted.

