9.5 TFL Layout

The layout of Tables, Figures and Listings (TFLs) will be according to the ICON IEB (former PRA EDS) standards.

Table shells are provided with and approved as part of this SAP. Small changes to shell layout due to the nature of the data may be required after lock at the discretion of the ICON lead biostatistician. Other changes to the shells may be out of scope. The TFLs will be provided as a single document in Adobe PDF format (in A4 format), and as individual files for each table, figure and listing in Rich Text Format (.rtf).

Format:

- Page size: A4
- Data in listings will be sorted by hepatic function group, subject number and time point.
- Data in tables will be sorted by hepatic function group and time point.

- Column titles will be in title case letters.
- All tables and listings will be in landscape format.
- The following hepatic function group labels will be used in the TFLs:
 - Normal
 - Mild
 - Moderate

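### AUC0-168h is a primary endpoint, but the planned ANOVA text does not name it, so no ratio or 90% CI is specified for it

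*SAP*

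**What the plan says.** SAP 5.1.1 lists three primary measures without ranking them: AUCinf (with AUClast as fallback), the "Area under the curve from time zero to 168 hours after" dosing, and Cmax. Protocol Section 3.1 and the protocol synopsis give the same list. The Part 1 primary objective (Protocol 2.1, SAP 5.1) is comparative: pharmacokinetics "in subjects with moderate hepatic impairment compared with matched control subjects with normal hepatic function".

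The comparison is an ANOVA on the log scale, which yields the GMR and its 90% CI. In SAP 16.2.2.1, Part 1, it is applied to "natural log transformed AUCinf or AUClast (if AUCinf cannot be calculated) and Cmax for apraglutide". For Part 2 it is applied to "natural log transformed AUCinf or AUClast and Cmax for apraglutide between normal hepatic function group from Part 1 (Reference") and the mild impairment group. The synopsis and Protocol 12.3.2.1 name the same two measures for both parts.

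AUC0-168h appears as a derived parameter in SAP 16.1.1.2, Table 3. SAP 16.2.2 provides individual values and descriptive statistics by hepatic function group for all calculated parameters, and Appendix 3 reports them in Table 14.2.1.2.

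For the interim, SAP 7.2 asks for "a table with at least the primary PK parameters and a table showing the GMR point estimate" of AUCinf (or AUClast) and Cmax. The same section gives only those two as the parameters needed.

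**The concern.** A primary measure under a comparative objective should have a stated between-group estimate. If the analysts follow the narrative, AUC0-168h gets group summaries only. If the table shells are also silent, a ratio and interval added at reporting would have to be identified in the CSR as unplanned under SAP 3.0. That is an awkward label for a primary endpoint.

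The measure is also not an obvious duplicate of the other AUC. Under SAP 7.2 and 16.2.2.1, a single subject with more than 20% extrapolation switches the GMR for everyone from AUCinf to AUClast, and AUClast ends at each subject's own last quantifiable sample. AUC0-168h is the only primary AUC defined over the same fixed window for all subjects, and that switch does not touch it. The window is 168/24 = 7 days, which matches the weekly dosing described in Protocol 1.2.3. The documents do not give this as the reason for choosing it; that link is my inference.

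**Working it through.** The question is one of specification. The plan gives no figure to reproduce, so the check sets the endpoint lists against every statement of the comparison.

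1. **Where AUC0-168h is declared primary:** protocol synopsis, Protocol 3.1 and SAP 5.1.1. All three include it.
2. **Where the ANOVA is described:** protocol synopsis, Protocol 12.3.2.1 and SAP 16.2.2.1, each for Parts 1 and 2. That is 3 × 2 = 6 statements, and none names AUC0-168h.
3. **Other comparative or graphical outputs:** the interim GMR table (SAP 7.2) and the box plots (synopsis, Protocol 12.3.2.1, SAP 16.2.2) also name only AUCinf or AUClast and Cmax.
4. **Any explanation for the omission:** none found. No section calls AUC0-168h descriptive only, and SAP 7.1 declares no changes from the protocol.

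Counting AUCinf/AUClast as one measure:

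| | Primary measures | Named in ANOVA text | Not named |
|---|---|---|---|
| Part 1 | 3 | 2 | 1 |
| Part 2 (if run) | 3 | 2 | 1 |
| Both parts | 3 × 2 = 6 | 2 × 2 = 4 | 6 − 4 = 2 |

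Both unnamed comparisons are AUC0-168h. Part 2 depends on a Part 1 GMR of at least 2, so the unconditional gap is the single one in Part 1.

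5. **What could still be recovered.** The model has one factor and no covariates (SAP 16.2.2.1 and 9.4.2). The estimate is therefore GMR = geometric mean (impaired) / geometric mean (normal), and both geometric means are planned for Table 14.2.1.2. The log-scale variance in each group follows from its geometric CV (as a fraction) as s² = ln(1 + CV²). With the group sizes, this gives the pooled variance and the 90% CI. The information is therefore not lost. There is one exception: SAP 16.2.2.1 drops the matched control of a moderate-group dropout from the Part 1 ANOVA, while the summaries use the full PK Parameter Set. After a dropout, the two sets of subjects could differ.

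**The case against.** The best counter-argument is that the plan is ambiguous rather than silent. The SAP pseudo-code runs by parameter on the whole parameter dataset without a filter, so run literally it would produce a GMR and 90% CI for AUC0-168h. Table 14.2.1.3 has a general title that excludes nothing. SAP 9.5 also says "Table shells are provided with and approved as part of this SAP", and those shells, which were not available for this review, may list the measure.

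The first two points do not settle the matter. The code is optional, and without a filter it would equally model tmax, for which SAP 16.2.2 allows only the median and range. Its Part 2 label refers to renal rather than hepatic function, so it is a poor basis for overriding explicit prose. The table title names no parameter. The shells are a real limit: if they list AUC0-168h, the consequence shrinks to a disagreement between shell and narrative within one approved plan. The same edit resolves it.

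It can also be argued that the omission is deliberate, since the same two measures recur throughout, and that little is at stake: no hypothesis is tested, no power was calculated, and the ratio can be recomputed. The low stakes are accepted. If the omission is deliberate, the plan should say so, because at present it presents AUC0-168h as an equal primary endpoint.

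**Conclusion.** The concern holds. In every narrative statement of the comparison, AUC0-168h is missing from the list of analysed measures despite being declared primary. This leaves one of three primary comparisons without a specified GMR and 90% CI in Part 1, and two of six over both parts.

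Confidence is high for what the text says. Whether the final report would actually lack the estimate depends on the unseen shells. No numerical effect on any result is claimed. The sample size, the Part 2 trigger and the absence of formal testing are unaffected. It should be fixed, because the correction costs almost nothing and lets the plan answer its primary question for all three measures.

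**What to change.** - **SAP 16.2.2.1, Parts 1 and 2:** extend the list of compared measures to log-transformed AUCinf (or AUClast), AUC0-168h and Cmax, with a GMR and 90% CI for each.
- **Table 14.2.1.3:** confirm that the shell includes AUC0-168h.
- **SAP 7.1:** record the addition, since this section now reports no changes from the protocol.
- **Part 2 trigger:** leave it on AUCinf/AUClast.
- **Tidying:** in SAP 7.2, state whether the interim parameter table needs AUC0-168h, and decide whether the box plots should show it.

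If AUC0-168h is intended as descriptive only, state that in SAP 5.1.1 instead, with the reason why a primary measure has no ratio.

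The core cost is two sentences, one line in SAP 7.1 and one shell check. The parameter is already derived, so no new data are needed. The SAP edit is enough for now, because SAP 3.0 says the SAP supersedes the protocol's statistical considerations. The synopsis and Protocol 12.3.2.1 can be aligned at the next amendment, since under Protocol 13.2.1 protocol changes generally need ethics committee approval.

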7.3 Final Analysis

Draft TFLs will be provided after database lock. After Sponsor comments have been incorporated, the TFLs will be finalized and incorporated in the first draft CSR.

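### The optional PROC MIXED pseudo-code sets neither a two-group subset nor a level order, so with three groups in ADPP at least one 'versus Normal' ratio would be wrong

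*SAP*

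**What the plan says.** SAP section 16.2.2.1 describes two comparisons in prose: moderate impairment (Test) against normal function (Reference) in Part 1, and mild impairment (Test) against normal function (Reference) in Part 2. Each is a Test minus Reference difference on the log scale with a 90% CI, exponentiated to a GMR. The prose also drops from the Part 1 analysis the normal subject matched to a moderate dropout, and lets that subject be used in Part 2 if there is a matched mild subject.

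Each part is then followed by code under the line "The following SAS PROC MIXED pseudo-code may be used". The elements that matter here are:

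- **Input:** "proc mixed data = adpp" in both blocks, processed by PK parameter only, with no WHERE statement or analysis flag.
- **Class variable:** "class hepatic_group", with no ordering option.
- **Contrast:** "hepatic_group 1 -1 /e cl alpha=0.1" in both blocks.
- **Labels:** "estimate 'Moderate hepatic impairment vs Normal hepatic function" in Part 1 and "estimate 'Mild hepatic impairment vs Normal renal function' hepatic_group" in Part 2.

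Three other places bear on this. The dataset table in section 9.2.4.1 lists a single ADPP, not one per part. Section 7.3 places the final outputs late: "Draft TFLs will be provided after database lock". Two group orderings appear. Section 9.5, under "The following hepatic function group labels will be used in the TFLs", lists Normal, Mild, Moderate. Section 9.2.2 numbers the cohorts 1 moderate, 2 normal, 3 mild.

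**The concern.** The same data, model and coefficients give the same answer. If ADPP holds three groups when the final outputs are made, the two blocks cannot return two different comparisons, yet one is labelled Moderate versus Normal and the other Mild versus Normal. A two-coefficient contrast is also positional: it compares whichever level comes first with whichever comes second.

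This is the only model code given for the primary GMRs and their 90% CIs. A mislabelled estimate here would misstate the effect of hepatic impairment on exposure, which is the trial's primary objective.

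**Working it through.** The plan states no figure on this point, so there is none to reproduce. The check applies the printed contrast to a one-way model on log exposure.

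**Inputs from the SAP.** Unfiltered ADPP; coefficients (1, -1); the group labels in 9.5; the cohort numbering in 9.2.2; about eight subjects per group (6.1).

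**Assumptions not in the documents.** SAS sorts class levels by their formatted value and sets a missing trailing coefficient to 0. The true ratios to Normal are illustrative: 2.0 for moderate (the Part 2 trigger value) and 1.4 for mild, with mild varied from 1.0 to 2.0.

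**Step 1, two groups only.** Printed ratio = exp(mean of first level - mean of second level). Sorted alphabetically, Moderate precedes Normal and Mild precedes Normal. The blocks then give 2.0/1 = 2.0 and 1.4/1 = 1.4, both correct. If Normal were instead coded first, the Part 1 block would give the inverse, 1/2.0 = 0.50.

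**Step 2, three groups.** The contrast becomes (1, -1, 0), and both blocks print the same ratio:

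| Level order | Where it comes from | Contrast | Printed in both blocks | Part 1 (2.0) | Part 2 (1.4) |
|---|---|---|---|---|---|
| Mild, Moderate, Normal | 9.5 labels, sorted | Mild - Moderate | 1.4/2.0 = 0.70 | wrong | wrong |
| Normal, Mild, Moderate | 9.5 labels, as listed | Normal - Mild | 1/1.4 = 0.71 | wrong | inverted |
| Moderate, Normal, Mild | 9.2.2 cohort numbers | Moderate - Normal | 2.0/1 = 2.0 | right | wrong |
| Normal, Moderate, Mild | other | Normal - Moderate | 1/2.0 = 0.50 | inverted | wrong |
| Mild, Normal, Moderate | other | Mild - Normal | 1.4/1 = 1.4 | wrong | right |
| Moderate, Mild, Normal | other | Moderate - Mild | 2.0/1.4 = 1.43 | wrong | wrong |

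No order makes both labels true. Part 2 is wrong under all three orders that the SAP suggests. In the first row, a true mild ratio between 1.0 and 2.0 prints as 1.0/2.0 = 0.50 to 2.0/2.0 = 1.00.

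**Step 3, check by fitting.** A least-squares fit to simulated data (eight per group, levels sorted alphabetically) returned 0.731 for (1, -1, 0), equal to the observed Mild/Moderate ratio. The coefficients (0, 1, -1) returned 1.978 and (1, 0, -1) returned 1.445, equal to the observed Moderate/Normal and Mild/Normal ratios.

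**Step 4, effect on interval width.** Keeping all three groups also pools the residual variance: 24 - 3 = 21 degrees of freedom instead of 16 - 2 = 14. The 90% CI multiplies and divides the GMR by exp(t × s × √(2/8)), with s = √ln(1 + CV²). At an assumed CV of 30% this factor is 1.287 with 21 df and 1.295 with 14. That effect is negligible; the problem is which means are compared.

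**The case against.** The best defence is that the code is offered as optional pseudo-code, while the binding prose names the right groups and the right direction. The matched-dropout rule already implies different subjects in the two parts, so a programmer following the text would build two-group inputs. On those, with the section 9.5 labels sorted alphabetically, the contrast is correct in both parts. The `/e` option prints the coefficients, LSMEANS prints each group mean, ADPP is double programmed (9.2.4.1) and the outputs are QC'd (9.2.4). Identical results under two labels would be hard to miss. The three-group case arises only if Part 2 is run.

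All of this stands and lowers the likelihood and severity. It does not supply the missing instruction: neither block contains a filter or the dropout exclusion, and nothing in the SAP fixes the order of the class levels.

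A reader might infer three stronger things that the documents do not support:

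- **That both blocks necessarily compute Mild minus Moderate.** This holds for one of six possible orders, the section 9.5 labels sorted alphabetically. The SAP does not say how `hepatic_group` is coded.
- **That the final Part 1 estimate is bound to be wrong once Part 2 data exist.** Under cohort numbering the Part 1 contrast is the intended one.
- **That the decision at a ratio of 2.0 is at risk.** Section 7.2 assigns that ratio to an interim report by the pharmacokineticist after Part 1, before a mild cohort exists, and does not refer to this code.

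**Conclusion.** The pseudo-code is incomplete in a way that matters only if Part 2 is run and the code is applied to the dataset it names. In that case at least one of the two primary 'versus Normal' GMRs, with its 90% CI, is wrong. That conclusion needs no assumption about SAS defaults, because the two blocks are identical apart from the label. Which estimate is wrong, and by how much, does depend on the level order and on the zero-fill rule. The printed values of 0.70, 0.71 and 2.0 also rest on the assumed ratios. If the trial stops after Part 1, the contrast is correct with alphabetical labels.

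Severity is minor to moderate: the intended analysis is clear from the prose and the error would probably be caught, but the code should match the text. The word 'renal' in the Part 2 label is a plain error.

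**What to change.** - **Subset each block.** Add a WHERE statement or analysis flag per part. Part 1: Moderate and Normal, with the matched-dropout exclusion built into the flag. Part 2: Mild and Normal, with the normal subjects eligible for that comparison.
- **Remove the dependence on level order.** Replace the positional ESTIMATE with a difference against the named reference, for example `lsmeans hepatic_group / diff=control('Normal') cl alpha=0.1`. If all three groups were kept in one model with levels sorted Mild, Moderate, Normal, the coefficients would have to be written out in full: 0 1 -1 for Moderate versus Normal and 1 0 -1 for Mild versus Normal.
- **Correct the Part 2 label** to read 'Normal hepatic function'.

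The cost is a few lines of SAP text, with no effect on subjects, data collection or the intended analysis. It should be done before database lock, for which SAP section 3.0 requires an approved and signed SAP. If the SAP is not reopened, the same three points can go into the programming specification for ADPP and the ANOVA table.
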